1.2 METHODS

Participants

All participants will be diagnosed as a stroke and will be recruited from the departments of the Neuromedical and Physical Medicine and Rehabilitation, Yangon General Hospital (YGH) and the National Rehabilitation Hospital (NRH) in Yangon, Myanmar. Eligible participants will be randomly allocated into either the experimental or control groups. For allocation of the participants, a computer-generated list of random number will be used. In order to maintain recruitment balance between groups throughout the trial, a permuted block randomization process will be used within each strata using block sizes of at least 2 with all blocks divisible by 2. The sequence generation and allocation concealment will be managed by the researcher. To prevent inadequate concealment of allocation sequence, properly randomizing method using sequentially numbered, opaque sealed envelopes (SNOSE) will be used in this study. The allocation envelope will be prepared by using the aluminum foil and carbon paper. The aluminum foil will be used to ensure opaque and the allocation sheet inside cannot read against the light. The carbon paper will be used to prevent violations of allocation concealment. The treatment allocation sheet of standardized-size paper will be fold to fit with envelop. Place 1 sheet of carbon paper on top of the folded allocation sheet with the carbon side facing the paper so that writing on the front of the envelop is transferred to the treatment allocation paper inside. Then place this carbon paper and allocation sheet together inside aluminum foil wrapper. Finally, place complete insert into the envelope properly (290). Group assignment will be communicated directly to the therapist for the implementation on a single participant basis. In this study, the assessments will be done by the researcher. The assessor and the participants will be blinded from the study.

Study Design

The study design will be a randomized double blind balanced parallel-group (1:1).

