1.5 PROCEDURE

All participants will be explained about details of the study and the interventions. After that, they will be asked to sign on the written consent approving by the committee of the institution prior to participate in study. All participants will be randomly allocated the participants into the experimental (SPCCT with MI) or the control (SPCCT with health education) groups. All participants will be screened following the criteria and will be collected the demographic data.

Both groups will receive the same program of SPCCT by physiotherapist who have 5 years experienced in neurological condition. Prior to training, tasks will be demonstrated using clear instructions. Seven lower extremity mobility tasks will be used in the SPCCT program. The tasks were selected from the study of Dean et al and adapted to be appropriate for improving gait function in patients with stroke. The trained tasks for the MI will be similar to the tasks in SPCCT to getting the transfer effects of training. The experimental group will receive MI training, whereas, the control group will receive health education which both will be provided by the researcher. Both groups will be matched for duration and frequency of the therapy sessions.

All outcome measures will be assessed by the therapist who have been trained the outcome measures of the study. As the primary outcome measurements, spatio-temporal variables will be measured by using two dimensional motion analysis method. The protocol of this method was proved to be valid and reliability from previous pilot study. For functional gait variables, six-minute walk test will be assessed for determining walking endurance, step test will be assessed for dynamic balance, and Timed Up and Go (TUG) test will be assessed for mobility function.

As the secondary outcome measure, the strength of hip flexor, hip extensor, knee flexor, knee extensor, ankle dorsiflexor, and ankle plantarflexor muscles will be assessed by using hand-held dynamometer. Muscle spasticity will be assessed by using the Modified Ashworth Scale (MAS). The outcome measures will be assessed at the baseline, after 2 weeks and 4 weeks intervention. For the safety, the therapist will measure blood pressure, pulse rate and fatigue level in the assessments, just before the training, and rest period during the training program.

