Stage 2 and 3: Visual and Kinesthetic Imagery

There will be 4 specific gait MI tasks (Table 3.2). For the stepping task, progression will be provided by number of repetitions provided by the rhythm of the metronome. For the walking tasks, progression will be increased by the number of walking repetition in the walkway. The practice of the tasks will be assigned serially. Each task will be taken for 2 minutes. During the training, number of repetitions will be noted after finish the tasks and will be entered into the log-book using as a feedback for the next

practice session. The engagements of the MI practice will be checked by the pulse rate using the oximeter attached to the fingers of the affected hand. The fingers movements of the unaffected hand will be recorded for numbers of repetitions of the task completion during imagine. Moreover, during the imagery practice, therapist will ask participants to stop imagine unexpectedly and check position in the practice.

Training schedule for MI

MI tasks	Duration (min)
1. Stepping forward and backward onto block	2
2. Standing up from a chair, walking a short distance (3 m), and returning to the chair	2
3. Symmetrical walking (8 m)	2
4. Walking at fast speed (8 m)	2

Stage 4: Refocusing of Body and Environment

The instructions of the MI training according to the stages are described in the following;

Stages	Tasks
Stage 1	Body relaxation and awareness.
Stage 2	
Visual imagery
 
Task 1. Stepping forward and backward onto blocks; 1.a Stepping forward and backward onto the block with the unaffected leg 1.b Stepping forward and backward onto the block with the affected leg
 
Task 2. Standing up from a chair, walking a short distance, and returning to the chair
 
Task 3. Symmetrical walking
 
Task 4. Walking at fast speed

Stage 3	
Kinesthetic imagery
 
Task 1. Stepping forward and backward onto blocks 1.a Stepping forward and backward onto the block with the affected leg 1.b Stepping forward and backward onto the block with the affected leg
 
Task 2. Standing up from a chair, walking a short distance, and returning to the chair
 
Task 3. Symmetrical walking
 
Task 4. Walking at fast speed

Stage 4	Refocusing of body and environment.

Health Education (HE)

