For the control group, they will receive 25 minutes of health education. The education will be provided by the researcher using the documents. One HE topic will take 2 treatment sessions and there will be 6 topics for the whole intervention period, 4 weeks. The training schedule for health education is described.

Topic	Duration (min)	Treatment session	Content
1. Changes caused by stroke	25	1 st and 2 nd	The most common general effects of stroke Common changes with a left-brain injury Common changes with a right-brain injury Common emotional effects of stroke Factors on which improvement depends
2. Complications after stroke	25	3 rd & 4 th	Common complications of stroke Treatments for complications after stroke
3. Emotional changes after stroke	25	5 th & 6 th	The way stroke cause emotional changes Some common emotional changes after stroke The way to cope changing emotion
4. Living at home after stroke	25	7 th & 8 th	Factors to going home Changes to do at home
5. High blood pressure (HBP) and stroke	25	9 th & 10 th	What is HBP? HBP and stroke risk Persons at higher risk for HBP.

Topic	Duration (min)	Treatment session	Content
6. Preventing recurrent stroke	25	11 th & 12 th	Controllable risk factors Uncontrollable risk factors Stroke warning signs

SPCCT

SPCCT program will include 7 different workstations intended to meaningful tasks related to gait performance. To get the effect of increasing therapy, it will involve the practice of higher levels of functional activities such as standing and walking. The training package will be provided according to participant's condition in terms of muscle strength and mobility status. The practice of the tasks will be serial in order. In the training the participants will be in the pairs. The practice will be as the distributed pattern. During the rest period of one participants who will observe the performance of partner and give encouragement to do the best. Each participant will receive activity log book in which the number of repetitions of performance will be entered and it will be used as the feedback in next station.

Training schedule of SPCCT is described in the following.

SPCCT details	Duration (min)
Warm up	3
1. Stepping forward-backward onto block	4 min practice, 4 min rest, 1 min transfer (9 min)
2. Stepping sideway onto block	9
3. Heel lifts in standing to strengthen affected planter-flexor muscles	9
4. Standing with a decreased base and reach for object	9

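### Nothing keeps the allocation from the physiotherapist who tailors SPCCT in both arms, so delivery of the shared training could differ by arm

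*Protocol*

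**What the plan says.** **Allocation and blinding (protocol 1.2, Participants).** "Group assignment will be communicated directly to the therapist for the implementation on a single participant basis". The same paragraph adds: "The assessor and the participants will be blinded from the study". The person who gives SPCCT is not on that list.

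**Who delivers what (protocol 1.5).** For the shared training: "Both groups will receive the same program of SPCCT by physiotherapist who have 5 years experienced in neurological condition". For the components that differ, the experimental group has MI and "the control group will receive health education which both will be provided by the researcher". The section also says: "Both groups will be matched for duration and frequency of the therapy sessions".

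**How SPCCT is set (protocol 1.6, SPCCT).** "The training package will be provided according to participant's condition in terms of muscle strength and mobility status". Participants train in pairs, and the resting partner observes and encourages. Each participant has a log book in which "the number of repetitions of performance will be entered and it will be used as the feedback in next station".

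**SAP.** It specifies a mixed repeated-measures ANOVA, or rank tests where normality fails. It contains no summary of delivered SPCCT by arm.

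**The concern.** The third specific objective compares MI plus SPCCT with HE plus SPCCT. The contrast isolates MI, against HE as the attention control, only if SPCCT is delivered alike in both arms. SPCCT is also the larger part of each session.

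The protocol calls SPCCT the same program, yet adapts it to each person's strength and mobility. Strength is a secondary outcome, and mobility function is measured by the Timed Up and Go test. In the protocol text, section 1.6 says how the MI tasks progress (metronome rhythm, number of walks) but gives no corresponding rule for the SPCCT stations. What the physiotherapist asks of a participant is therefore a matter of judgement. If that judgement is made with knowledge of the arm, a between-arm difference in gait could come partly from how SPCCT was given. Blinding the assessor does not protect against this, because the difference would be real and would arise before measurement.

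**Working it through.** **1. Who could know the arm.** The relevant statements, side by side:

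- 1.2: the allocation goes to a therapist, for implementation. The researcher manages the sequence and its concealment, and also does the assessments.
- 1.5: the researcher provides MI and HE; a physiotherapist provides SPCCT; a trained therapist does the assessments.
- 1.6, MI training: a therapist leads the relaxation stage and checks engagement, as in "during the imagery practice, therapist will ask participants to stop imagine unexpectedly and check position in the practice".

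So the word therapist may mean the SPCCT physiotherapist, the person running MI, or the assessor. If it is the SPCCT physiotherapist, the arm is disclosed outright. If it is the person running MI, no statement withholds the arm from the SPCCT physiotherapist. If it is the assessor, that contradicts the blinding statement and still leaves the SPCCT physiotherapist unaddressed. The gap is present on all three readings.

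**2. What is fixed by the schedule (1.6).**

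- SPCCT per session: 3 + 6 × 9 + 8 = 65 min, which reproduces the stated total.
- MI block: 3 + 8.5 + 2 + 8.5 + 3 = 25 min, equal to the 25 min of HE.
- Session: 25 + 65 = 90 min, as stated; SPCCT is 65/90 = 72% of it.
- Station practice: 7 × 4 = 28 min per session. With 3 × 4 = 12 sessions, 28 × 12 = 336 min in each arm.

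Scheduled minutes, stations and frequency therefore cannot differ by arm under the plan.

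**3. What is not fixed.** Within each 4-minute slot, the number of repetitions, the difficulty, the rate of progression and the encouragement are open. The four MI tasks correspond to SPCCT stations 1, 5, 6 and 7, which is 4 × 4 = 16 of the 28 practice minutes per session. A physiotherapist who knows the arm also knows which stations a participant has been rehearsing. Those stations resemble measured outcomes (step test, Timed Up and Go, walking).

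**4. What a shift would do (illustration).** The documents give no estimate of arm-related drift, so its size is assumed over a range.

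- Inputs: 20 per arm (15 + 5 and 11 + 9, protocol summary); level 0.05 (SAP), taken as two-sided because sidedness is not stated; true MI effect zero; drift moves the outcome mean in one arm by d SD.
- Method: two-sample t-test, 20 + 20 − 2 = 38 degrees of freedom, noncentrality d/√(2/20) = d/0.316. This stands in for the planned ANOVA.

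| Assumed d (SD) | Noncentrality | Chance of p < 0.05 | Normal approximation |
|---|---|---|---|
| 0 | 0 | 5.0% | 5.0% |
| 0.1 | 0.316 | 6.1% | 6.15% |
| 0.2 | 0.632 | 9.5% | 9.69% |
| 0.3 | 0.949 | 15.2% | 15.78% |
| 0.5 | 1.581 | 33.8% | 35.26% |

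The two-sided figures are the same whichever arm is favoured. If the drift favoured HE while MI did work, it would hide part of the effect.

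**The case against.** The strongest reply is that the therapist in 1.2 may simply be the person who runs MI, since 1.6 uses the word that way. The allocation would then already go where it should. This stands in part: a reader might infer that the protocol discloses the arm to the SPCCT physiotherapist, and no sentence says so. What remains is that no sentence withholds it either, and that role names which conflict across 1.2, 1.5 and 1.6 cannot be relied on to do so.

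Second, the protocol matches the arms for duration and frequency and fixes the stations. This also stands. A reader might infer that the SPCCT dose as a whole could drift, or convert a percentage difference in repetitions into minutes of practice. Neither is supported: any difference occurs inside equal 4-minute slots.

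Third, the Borg exertion criterion (1.3) and the checks of blood pressure, pulse and fatigue (1.5) apply to both arms and limit how far intensity can be pushed. They narrow the room for drift but do not make delivery equal below those limits.

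Fourth, more repetitions in the MI arm need not mean unequal delivery. The MI tasks were chosen to resemble the SPCCT tasks so that training would transfer, so extra repetitions may be a route by which MI works. This is correct and limits what the log book can show. A reader might want to credit MI only when repetitions are similar. That would condition on a post-randomisation variable and could discard a genuine effect.

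**Conclusion.** The concern holds as a gap in the plan. The SPCCT physiotherapist does not need the allocation under 1.5, is not listed as blinded, tailors the shared training by judgement, and is not kept from knowing the arm on any reading of the text. Repetitions, difficulty, progression and encouragement could therefore differ by arm and confound the third objective.

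It is a risk, not a demonstrated bias, and its size is unknown. The 6.1% to 33.8% range rests on assumed shifts of 0.1 to 0.5 SD, zero MI effect, 20 per arm and a simple t-test in place of the planned analysis. A reader might also infer that the bias would favour MI. The documents do not support a direction, since a physiotherapist might equally compensate participants who receive only education. Nor is SPCCT the only physical practice: the first-week MI familiarisation also has participants perform the tasks physically, so equal SPCCT would not by itself guarantee that the arms differ only in imagery.

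**What to change.** - **Protocol 1.2:** state that the allocation goes only to the person who delivers MI or HE, and that the SPCCT physiotherapist is not told the arm and sets and progresses each package without that knowledge. List that physiotherapist with those kept unaware.
- **Protocol 1.2, 1.5 and 1.6:** reconcile therapist and researcher, so that each task (holding the allocation, MI and HE, SPCCT, assessment) has one named role. The person who delivers MI or HE cannot also be the blinded assessor, as 1.2 and 1.5 read together would now allow.
- **SAP:** add a descriptive table of logged SPCCT repetitions by station, week and arm. State that a difference may reflect unequal delivery or an effect of MI, and do not make attribution to MI conditional on it.

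The cost is a few sentences and one table from data already recorded. No extra staff are needed if the division of roles in 1.5 is kept. The drawback is that masking will be partial: participants may reveal their arm, the more so because they train in pairs. Repetition counts also say nothing about difficulty or encouragement. The protocol summary is partly in the past tense. If treatment has already been delivered, masking can no longer be changed, but the physiotherapist's awareness of the arm can be reported and the table made from retained log books.

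### The protocol names two different outcome assessors, and neither version supports assessor blinding or the double-blind label as written

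*Protocol*

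**What the plan says.** Protocol section 1.2 (Participants) gives the researcher two tasks. On allocation: "The sequence generation and allocation concealment will be managed by the researcher". On outcomes: "In this study, the assessments will be done by the researcher. The assessor and the participants will be blinded from the study". It also says: "Group assignment will be communicated directly to the therapist for the implementation on a single participant basis". Under Study Design it concludes: "The study design will be a randomized double blind balanced parallel-group (1:1".

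Section 1.5 distributes the work differently. Circuit training has its own provider: "Both groups will receive the same program of SPCCT by physiotherapist who have 5 years experienced in neurological condition". For motor imagery (MI) and health education (HE), it says "the control group will receive health education which both will be provided by the researcher"; section 1.6 repeats this for HE. For outcomes it says: "All outcome measures will be assessed by the therapist who have been trained the outcome measures of the study". For safety checks, "the therapist will measure blood pressure, pulse rate and fatigue level in the assessments, just before the training, and rest period during the training".

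Section 1.6 also has a therapist lead parts of the MI sessions: the relaxation stage, and the unannounced checks during imagery. The SAP does not mention blinding.

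**The concern.** The two sections disagree on who assesses outcomes. If section 1.2 is followed, the assessor runs allocation and delivers the component that distinguishes the arms. If section 1.5 is followed, the assessor holds a role title that elsewhere receives the assignment and takes part in training.

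This matters because most of the outcomes are open to influence. The Timed Up and Go, six-minute walk and step test depend on instruction and encouragement. Hand-held dynamometry and the Modified Ashworth Scale depend on the tester's technique and judgement. The primary spatio-temporal variables come from video and are probably less exposed, but they still depend on patient effort and on whoever measures the recording. If the assessor knows the arm, detection bias could be read as an MI effect, and no analysis of the resulting data could tell the two apart. The double-blind label would tell readers that this risk had been controlled.

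**Working it through.** **Roles set side by side**

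| Task | Section 1.2 | Sections 1.5 and 1.6 |
|---|---|---|
| Sequence and concealment | researcher | – |
| Told the assignment | the therapist, for implementation | – |
| Delivers MI and HE | – | researcher (1.5; 1.6 repeats HE); a therapist leads parts of MI (1.6) |
| Delivers circuit training | – | experienced physiotherapist |
| Assesses outcomes | researcher, with the assessor called blinded | a therapist trained in the outcome measures |
| Safety measurements at assessments and in training | – | the therapist |

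*Reading 1: the researcher assesses.* Both arms receive the same circuit programme, so MI versus HE is what defines the arm. Whoever delivers MI to one patient and HE to another knows both assignments. The blinding statement cannot then be true.

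*Reading 2: the trained therapist assesses.* Section 1.5 describes this person separately from the circuit-training physiotherapist, which points towards a separate assessor. But neither document says that the assessing therapist differs from the one told the assignment, the one taking safety measurements during training, or the one taking part in MI. Neither says that assignment is withheld from the assessor. Blinding is possible but not secured.

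*Participants.* Section 1.5 has the study and the interventions explained to them, and they know which they receive. HE is matched to MI for duration and frequency, so they could have been kept unaware of the hypothesis, but the protocol does not say so.

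**Illustration of size**

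The documents give no figure for assessor bias. The shift and the correlation ρ below are assumptions.

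Inputs: 20 per arm (section 1.1: 15+5 and 11+9); three assessments; the SAP's two-way mixed ANOVA at 5%; compound symmetry; no shift at baseline. Let d be the arm difference, in SD units, at baseline, week 2 and week 4.

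- Group-by-time test: F(2, 76), since 2×(40−2) = 76; noncentrality λ = 10·Σ(d_t − d̄)²/(1−ρ).
- Group main effect: F(1, 38); λ = 10·d̄²/((1+2ρ)/3).

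Worked example: d = (0, 0.1, 0.2) has d̄ = 0.1 and Σ(d_t − d̄)² = 0.02. At ρ = 0.5, λ = 10×0.02/0.5 = 0.4 and the rejection rate is 0.080. At ρ = 0.9, λ = 2.0 and the rate is 0.218.

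Group-by-time rejection rate with no true MI effect (nominal 0.05):

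| d | ρ=0.5 | 0.6 | 0.7 | 0.8 | 0.9 |
|---|---|---|---|---|---|
| (0, 0.1, 0.2) | 0.080 | 0.088 | 0.101 | 0.129 | 0.218 |
| (0, 0.2, 0.2) or (0, 0, 0.2) | 0.091 | 0.101 | 0.120 | 0.158 | 0.280 |
| (0, 0.15, 0.3) | 0.121 | 0.140 | 0.173 | 0.241 | 0.445 |
| (0, 0.3, 0.3) or (0, 0, 0.3) | 0.147 | 0.173 | 0.218 | 0.310 | 0.566 |

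The group main effect moves less: 0.055–0.080 for 0.2 SD and 0.062–0.118 for 0.3 SD. Simulation with 40,000 replicates per setting agrees: 0.051 under the null at ρ = 0.5 and at ρ = 0.9; 0.082 and 0.216 for d = (0, 0.1, 0.2) at those two correlations; 0.566 for d = (0, 0.3, 0.3) at ρ = 0.9.

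**The case against.** The best reply is that section 1.5 is the specific text on outcome assessment and reflects the intent. It names a therapist trained for the task and describes the circuit-training physiotherapist separately, while section 1.2 sends assignment to the therapist for implementation, which suggests treating staff. The sentence making the researcher the assessor could be a drafting slip. Role titles may also cover several people. This is plausible, and it is why the finding goes no further than unsupported as written. It does not supply the missing statement that the assessor is separate and uninformed.

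Three narrower points stand:

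- Managing the sequence would not by itself unblind the researcher, because opaque envelopes could keep individual assignments hidden. Delivering MI and HE is what does it.
- Participant blinding is a softer point. The documents do not contradict it outright, and it is mainly a matter of labelling.
- The illustration says nothing about what happened in this trial. Its top figure, 0.566, needs a 0.3 SD shift at ρ = 0.9. There the SD of change is √(2×0.1) = 0.45, so the shift is about 0.67 SD of change, an extreme case. The illustration also covers only the ANOVA route, whereas the SAP sends non-normal variables to rank tests, the likely route for the Modified Ashworth Scale.

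**Conclusion.** The concern holds and needs to be fixed. Sections 1.2 and 1.5 name different assessors. Under the first, assessor blinding is impossible; under the second, it is not secured. Nothing elsewhere in the protocol or in the SAP resolves this, so the double-blind label is unsupported.

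This conclusion comes from the text and needs no numerical assumption. The illustration shows only that a modest bias could matter at this sample size: a group-by-time false-positive rate of about 8–28% for a 0.2 SD shift and 12–57% for 0.3 SD. Those ranges are conditional on the assumed shift, ρ between 0.5 and 0.9, and compound symmetry. Correlation drives most of the range: a 0.2 SD shift that builds linearly goes from 8% to 22% as ρ rises from 0.5 to 0.9. The shape of the shift matters less. At ρ = 0.7, a full shift from week 2 gives 12% against 10% for a linear one; at ρ = 0.9 the figures are 28% and 22%.

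**What to change.** 1. **Establish whether assessments are finished.** The past tense and arm-level data in section 1.1 suggest that they are. If so, deleting the sentence in section 1.2 would hide the problem. Report who assessed at baseline, week 2 and week 4, and what they knew of allocation. If gait recordings were kept, have them measured under coded IDs by someone who does not know the arm.
2. **If assessments are still to be done,** remove the statement that the researcher assesses and make the trained therapist of section 1.5 the only assessor. State that this person has no part in sequence generation, envelopes, MI, HE or circuit training and is not told assignment. Code gait videos before they are measured.
3. **Correct the label.** Use assessor-blinded only if the conditions in step 2 were met; otherwise state that the trial is not assessor-blinded. Say that participants knew which intervention they received, and what, if anything, about the hypothesis was withheld.
4. **Clarify the therapist in the MI sessions of section 1.6:** is this the researcher who provides MI under section 1.5, or someone else?

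The cost is wording, plus some role scheduling if assessments remain. The documents give no staffing numbers, so a separate assessor may not be available; the honest label is then the remedy. If assessments are complete, the cost is disclosure, possibly re-measurement of kept videos, and perhaps a less favourable design label.
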